### 9.7. Treatment Compliance

Patient compliance with study medication will be assessed at each visit. Compliance will be assessed by direct questioning, review of diary, and counting returned tablets. Deviations from the prescribed dosage regimen should be recorded in the “Study treatment: modifications” form.

For patients who are significantly noncompliant (<80% or >120% of expected study drug taken in a visit interval), investigative sites must counsel patients on the importance of study drug compliance and drug accountability. Patients who are consistently out of the compliance range may be discontinued. A Lilly representative should be contacted upon the second instance of treatment noncompliance.

The following procedures will be employed to ensure appropriate drug accountability:

- Drug accountability will be emphasized at the start-up meeting.
- Drug accountability will be monitored throughout the study.
- Each patient should be instructed to return all study-drug packaging and unused material to the study site at each visit. The study site will keep a record of all drug dispensed to and returned by the patients throughout the study. Study site personnel will return or destroy (as requested) all unused study drug for all patients.

Patients will keep a study diary to document that they are taking LY2157299/  
LY2157299-matched placebo and sorafenib correctly.

## 10. Efficacy, Health Outcome/Quality of Life Measures, Safety Evaluations, Sample Collection and Testing, and Appropriateness of Measurements

Terms used to describe the periods during the study are defined below:

- **Baseline (Visit 0):** From the time of screening to the first study treatment (or discontinuation, if no treatment is given)
- **Treatment Start:** First day of study treatment
- **Treatment Period:** Time from treatment start to discontinuation from study treatment
  - During the study period, cycle number will correspond to visit number (eg, Cycle 1 = Visit 1).
  - During the extension period, cycle number will correspond to extension visit number (eg, Cycle 1 = Visit 501).
- **Discontinuation from Study Treatment:** The day the patient discontinues study treatment (summary visit)
  - applies to patients in extension period, too
- **30-Day Safety Follow-Up Period (Visit 801):** The time after the patient discontinues study treatment during which follow-up data are collected. Visit 801 starts 1 day after discontinuation from study treatment and lasts 30 days ( $\pm 3$  days).
  - applies to patients in extension period, too. However, for patients in the extension period, the end of the 30-day safety follow-up period is also the end of their study participation (unless further follow-up is required for cardiac toxicities).
- **Long-Term Follow-Up Period (Visits 802, 803, etc):** Visit 802 starts 1 day after the 30-day Safety Follow-up (Visit 801) and lasts 60 days ( $\pm 7$  days). All subsequent long-term follow-up visits will occur at 60-day intervals ( $\pm 7$  days) (for example, Visit 803, Visit 804, etc.) for as long as the patient remains alive or until the required number of deaths have been observed.
  - not required for patients in extension period unless there are cardiac toxicities

Written informed consent must be obtained prior to any study-specific pretreatment evaluations.

Study procedures related to efficacy, safety, health outcome/quality of life measures, sample collection and testing assessments and their timing are described in the sections below and are shown in the Study Schedule ([Attachment 1](#)).

### 10.1. Efficacy Measures

All patients will be followed for progression and OS. Patients who come off therapy due to objective progressive disease will be followed for survival every 2 months. Patients may continue on study treatment even if they have objective progression or if they are clinically asymptomatic (see Section 7.3). However, it is important that the cycle response records

objective progressive disease in the cycle that it occurred in order to estimate TTP, PFS, and response rate without bias. These patients will then be discontinued from study treatment because of overall symptomatic deterioration (including biomarker response) or other causes. Patients who come off therapy and do not have objective progressive disease should be followed every 2 months after discontinuation from study treatment until death, including radiologic examinations every 6 weeks until objective progressive disease is determined (using the same radiological scans as at baseline). Patients who progress should then be followed for survival every 2 months. Every attempt should be made to gather all information every 2 months (radiological scans and survival), even if a patient starts a new anticancer therapy. Evaluation of survival can be accomplished by telephone contact if necessary. The date any new anticancer therapy starts, either during the 30-day safety or long-term follow-up periods, needs to be collected. This will enable a better estimate of time-to-event data to inform future decisions in this indication as it will be based on more mature data.

It is important that protocol procedures related to collection of these data, both during the active study treatment phase and follow-up period, are followed and that dates of data collection are recorded accurately.

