**Test Product, Dosage, and Mode of Administration**

LY2157299 will be administered orally by daily dosing morning and evening (twice daily [BID]). The monotherapy dose will be 150 mg BID (300-mg daily dose) for 14 days, followed by 14 days with no study drug. The LY2157299 dose used in combination with sorafenib will be determined based on the results of the H9H-MC-JBAK (JBAK) study Part C (dose will either be 80 mg or 150 mg BID [160 mg or 300 mg daily dose]) for 14 days, followed by 14 days with no study drug.

LY2157299-matched placebo will be administered orally by daily dosing morning and evening (BID) for 14 days, followed by 14 days with no placebo.

Sorafenib will be administered orally by daily dosing morning and evening (BID) at 400 mg per dose (total dosage of 800 mg daily) for 28 days.

One cycle is defined as 28 days in all treatment arms.

**Planned Duration of Treatment Per Patient:** Patients will receive LY2157299 until their disease has progressed, the patient has died, or the patient discontinues for adverse events, investigator's judgment, or other reasons.

**Wash-out period:** none.

**Planned Follow-up Observation Period Per Patient:** Patients who have discontinued study treatment without progression will continue to be followed for progression. Every attempt should be made to gather all information every 2 months (radiological scans and survival), even if a patient starts a new anticancer therapy. All patients will be followed until death. Patients who have entered the treatment extension period will be followed for just 30 days after treatment discontinuation.

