#### **10.3.2.2. Echocardiographs with Doppler and Chest Computed Tomography Scans**

Because of the cardiotoxicity monitoring in this study, echocardiographs with Doppler and chest CT scans are being performed (see [Attachment 1](#), [Attachment 14](#), and [Attachment 15](#)).

Echocardiography with Doppler will be locally assessed at screening for enrollment and throughout the study according to the Study Schedule ([Attachment 1](#)) for safety decisions by a physician or a person who is qualified by experience or training. The individual must be identified at each site. A central reading will be performed for the data used in the study report.

Chest CT scan with contrast of thorax and abdomen to evaluate the large vessels of the heart will be locally assessed at screening for enrollment and every 6 months throughout the study and at the end of study visit (Visit 801) according to the Study Schedule ([Attachment 1](#)) for safety decisions by a physician or a person who is qualified by experience or training. Alternatively, chest and/or abdomen MRI are allowed.

Chest CT scan with contrast of thorax and abdomen for tumor assessment will be locally assessed at screening for enrollment and every 6 weeks starting Cycle 2 Day 14 until radiological disease progression according to the Study Schedule ([Attachment 1](#)) by a physician or a person

who is qualified by experience or training. Alternatively, chest and/or abdomen MRI are allowed.

If the patient has clinically significant cardiac findings at discontinuation (Visit 801), echocardiography, ECG and ECG chemistry will be repeated every 2 months for 6 months (Visits 803, 804, and 805).

If there are no clinically significant cardiac findings at discontinuation (Visit 801), 1 more echocardiography, ECG, and ECG chemistry will be performed after 2 months (Visit 802). If a patient receives another treatment, Visit 802 cardiac assessments will not be performed.

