## **Attachment 1. Protocol JBAS Study Schedule**

---

Study Schedule, Protocol H9H-MC-JBAS – Study Period

Cycle (Visit)	Baseline (Visit 0)			Patient on Study Treatment									Post Discontinuation Follow-Up Periods		Comments	
				Cycle 1 (Visit 1)			Cycle 2 (Visit 2)			Cycle 3, n a (Visit 3, etc)			30-Day Safety Follow-Up (v801)	Long-Term Follow-Up b (v802, v803, etc)		
Relative Day Within a Cycle	≤28	≤14	≤7	1c,d	8c	14c	15	22	1c	14c,e	22	1c			14c,e	
Procedures																
Informed consent	X															Informed consent must be signed prior to performing any study procedures.
Medical history		X														
Child-Pugh, BCLC, and CLIP staging			X f													
Physical exam including vital signs (heart rate, blood pressure, weight)		X		X		X			X	X		X		X		Starting in Cycle 3, to be performed once per cycle
CTCAE grading		X		X		X			X	X		X		X	X g	Starting in Cycle 3, to be performed once per cycle
Concomitant medications		X		X					X			X	X	X	X	During long-term follow-up collect only therapy provided to patient for HCC
ECOG performance status		X		X		X			X	X		X		X		Starting in Cycle 3, to be performed once per cycle
Survival data														X		Every 60 days ±7 days

Cycle (Visit)	Baseline (Visit 0)			Patient on Study Treatment									Post Discontinuation Follow-Up Periods		Comments	
				Cycle 1 (Visit 1)			Cycle 2 (Visit 2)			Cycle 3, na (Visit 3, etc)			30-Day Safety Follow-Up (v801)	Long-Term Follow-Up b (v802, v803, etc)		
Relative Day Within a Cycle	≤28	≤14	≤7	1 c,d	8 c	14 c	15	22	1 c	14 c,e	22	1 c			14 c,e	
Tumor assessment, physical (palpable or visible)		X		X					X			X		X		
Imaging procedures																
Echocardiography with Doppler h	X								X			X		X i	X i	Cycle 2, 3, 4, and every other cycle (Cycle 6, Cycle 8, etc)
Chest CT scan or Chest MRI		X												X j		CT scan or MRI every 6 months (for cardiac assessment)
Tumor assessment, radiological		X								X			X	X k	X k	Chest CT scan with contrast of thorax and abdomen ( with both arterial and portal phase imaging of the liver for mRECIST) or MRI for tumor assessment every 6 weeks (± 3 days) starting Cycle 2 Day 14
ECG		X							X			X		X i	X i	Cycle 2, 3, 4, and every other cycle (Cycle 6, Cycle 8, etc)

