Abbreviations: AFP = alpha-fetoprotein; aPTT = activated partial prothrombin time; BCLC = Barcelona Clinic Liver Cancer; BNP = brain natriuretic peptide; BSC = best supportive care; C = cycle; CLIP = Cancer of the Liver Italian Program; CT = computed tomography; CTCAE = Common Terminology Criteria for Adverse Events; DCE-MRI = dynamic contrast-enhanced magnetic resonance imaging; DW-MRI = diffusion-weighted magnetic resonance imaging; ECG = electrocardiogram; ECOG = Eastern Cooperative Oncology Group; eGFR = estimated glomerular filtration rate; EORTC = European Organisation for Research and Treatment of Cancer; exam = examination; GBCA = gadolinium-based contrast agent; HBsAg = hepatitis B surface antigen; HCC = hepatocellular carcinoma; INR = international normalized ratio; MAP = multi-analyte panel; mRECIST = modified Response Evaluation Criteria in Solid Tumors; MRI = magnetic resonance imaging; PF4 = platelet factor 4; PGx = pharmacogenomics; PIVKA II = prothrombin induced by vitamin K absence; PK = pharmacokinetic; PT = prothrombin time; QLQ = quality-of-life questionnaire; RNA = ribonucleic acid; TGF- $\beta$  = transforming growth factor beta.

- a Patients on study for more than 1 year (before entering extension period) only need tests to be performed on Day 1 of each cycle.
- b Follow-up consists of Visit 802 and all subsequent visits (60 days  $\pm$  7 days).
- c To be performed predose LY2157299 or sorafenib
- d A delay at the start of a cycle (Day 1) of no more than 3 days because of holidays, weekends, inclement weather, or other justifiable events will be permitted and not counted as a protocol violation.
- e In extenuating circumstances, the “on study drug” window for LY2157299 is allowable from Day 10 to Day 14.
- f Child-Pugh, BCLC, and CLIP assessment procedures can be found in [Attachment 6](#), [Attachment 7](#), and [Attachment 8](#), respectively.
- g If drug-related toxicity is present 30 days after the last cycle of study drug, patients must be followed up approximately every 30 days until toxicity resolution, stabilization, another therapy is initiated, or death.
- h Echocardiography with Doppler can be performed up to 3 days prior to Day 1.

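### For patients who stop drug without progression, the protocol gives two incompatible tumor-scan intervals, and the first on-treatment scan moves with any delay of Cycle 2

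*Protocol*

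**What the plan says.** **Off treatment, no progression.** Protocol Section 10.1 wants these patients seen every 2 months until death, "including radiologic examinations every 6 weeks until objective progressive disease is determined". Later in the same paragraph, and again in the synopsis under the follow-up period, stands: "Every attempt should be made to gather all information every 2 months (radiological scans and survival), even if a patient starts a new anticancer therapy". The synopsis has no 6-week rule for these patients. In Attachment 1 the radiological tumor row is marked at Visit 801 and in the long-term follow-up column. Footnote b defines that column: "Follow-up consists of Visit 802 and all subsequent visits". Section 10 fixes the spacing: "All subsequent long-term follow-up visits will occur at 60-day intervals".

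**On treatment.** Section 10.3.2.2 sets tumor scans "every 6 weeks starting Cycle 2 Day 14 until radiological disease progression". The comment on the Attachment 1 row agrees: "or MRI for tumor assessment every 6 weeks (± 3 days) starting Cycle 2 Day 14". SAP Section 6.12.7.3 repeats this rule. In the same row the generic Cycle 3,n column is marked at Day 14. Footnote a adds: "Patients on study for more than 1 year (before entering extension period) only need tests to be performed on Day 1 of each cycle".

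**Endpoints.** Protocol Table JBAS.10.1 and SAP Section 6.9 start TTP and PFS at randomization. SAP Section 6.9.2.2 reports medians, rates at 3, 6, 9 and 12 months, and pairwise hazard ratios. Both endpoints are secondary.

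**The concern.** Progression can be dated only at a scan. If the scan calendar depends on whether a patient is still on drug, or on when Cycle 2 began, the recorded date depends on treatment course as well as on disease. If delay or early stopping then differs between arms, part of any difference in TTP or PFS reflects scan timing.

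There is also a practical cost. SAP Appendix 1 counts a tumor assessment that was not done as a significant violation, and SAP Section 6.12.9 lets such violations remove a patient from the per-protocol population. In the first 180 days off drug, 6-weekly scans counted from stopping fall on days 42, 84, 126 and 168, four in all. The marked visits fall on about days 30, 90 and 150, three in all. A monitor cannot say whether a scan is missing until one rule is chosen.

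**Working it through.** **The plan's own figures.** The documents give no sample size, event count or power for TTP or PFS. The nearest stated figure is the log-rank power for OS of 73% (Protocol Section 12.1). Exponential hazards (control 0.0216/week, HR 0.667), 10 patients per month and 104 weeks of minimum follow-up give 78.7 deaths in the two arms. With 1/3 of those patients on control, √(78.7 × 2/9) × |ln 0.667| − 1.080 = 0.613 and Φ(0.613) = 0.730. The figure is reproduced and uses no scan date, so nothing below touches OS.

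**On-treatment calendar.** I count from Cycle 1 Day 1 and assume randomization on the same day.
- 28-day cycles: Cycle 2 Day 14 is day 28 + 14 = 42, exactly 6 weeks. Later scans fall on days 84 (Cycle 3 Day 28), 126 (Cycle 5 Day 14) and 168 (Cycle 6 Day 28). Only every second scan lands on a Day 14.
- Cycle 1 of 26 to 31 days, the stated limits: first scan on day 40 to 45.
- Cycle 2 start delayed 14 days: scans on days 56, 98, 140 and 182. Delayed 30 days: first scan on day 72.

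**Landmark rates.** The 3-month landmark is 3 × 30.44 = 91.3 days. The apparent progression-free rate there is the true rate at the last scan before it. With exponential TTP, S(d) = 2^(−d/M), where M is the median. Protocol Section 5 gives sorafenib medians of 2.8 months (Asian trial; M = 85.2 days) and 5.5 months (US/EU trial; M = 167.4 days).

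| Median TTP | No delay: S(84) | 2-week delay: S(56) | Gap |
|---|---|---|---|
| 2.8 months | 50.5% | 63.4% | 12.9 points |
| 5.5 months | 70.6% | 79.3% | 8.7 points |

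The gap applies to delayed patients. If 10% to 30% of an arm were delayed (assumed), the arm's rate would move by 0.10 × 12.9 = 1.3 to 0.30 × 12.9 = 3.9 points at the 2.8-month median. For scale, the standard error of a difference between rates near 50% in arms of 60 and 30 is √(0.25/60 + 0.25/30) = 11 points.

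The second scan crosses the landmark only if the delay exceeds 91.3 − 84 = 7.3 days. Within the cycle limits it falls by day 87, or day 90 at the end of the ±3-day window, so ordinary slippage does not trigger the effect. At 6 months (182.6 days) the sign reverses: the last scan is day 168 without delay and day 182 with it, so at the 2.8-month median the apparent rate falls from 25.5% to 22.8%.

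**Off-treatment interval.** With λ = ln 2/85.2 and scans every 42 days, the mean lag from progression to detection is 42/(1 − e^(−42λ)) − 1/λ = 22.2 days. For patients progression-free at stopping, a scan at 30 days and then every 60 gives 30 + 60e^(−30λ)/(1 − e^(−60λ)) − 1/λ = 28.8 days. A simulation of 200,000 patients, with stopping spread evenly over days 14 to 120 (assumed), gives about 22 and 31 days. Averaged over an arm with 20% to 40% at risk of early stopping (assumed), detection is 1.3 to 2.7 days later.

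**Hazard ratio under early stopping.** The simulation used 20,000 patients per arm and the same true exponential TTP in both (median 2.8 or 5.5 months). One arm stayed on 6-week scans. In the other, a fraction stopped on days 28 to 84 without progression (assumed) and moved to the Visit 801 and 60-day calendar.

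| Fraction stopping | HR, 2.8 months | HR, 5.5 months |
|---|---|---|
| 10% | 1.005 | 0.998 |
| 25% | 0.984 | 0.982 |
| 50% | 0.971 | 0.972 |

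The Monte Carlo standard error of each log HR is about √(2/20,000) = 0.010.

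**The case against.** Much of the case on the other side stands.

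- *The schedule already settles the on-treatment rule.* A reader might infer a third clock from the Day 14 mark in the Cycle 3,n column. The documents do not support that. The column is generic, the row's comment sets 6 weeks, and echocardiography in the same table is also marked under Cycle 3,n while its comment sets a sparser frequency.
- *Footnote a need not cover scans.* A reader might infer that tumor scans stop, or move to Day 1, after a year. The footnote speaks of tests, the schedule separates imaging procedures from laboratory tests, and Section 10.3.2.2 has no one-year limit. This is an ambiguity, and at a 2.8-month median only 2^(−12/2.8), about 5%, would still be progression-free then.
- *No difference between arms is shown.* A reader might infer that the combination arm is scanned later and so looks better. The documents give no delay or stopping rates, Arms 2 and 3 share one blinded schedule, and one drug may continue while the other is held, so a dose delay need not move the cycle. A difference is most plausible for Arm 1, which is open label and has no sorafenib. Nor is the direction fixed, as the 6-month reversal shows.
- *The SAP limits the damage.* Progression counts only before new anticancer therapy, and SAP Version 2 removed visit timing from the violation list. The first limit is partial: TTP is censored at the last assessment before new therapy or death, so sparser scans can also turn progressions into censored times.

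It might also be said that the Attachment 1 comment, with Section 10.1.1 deferring to the Study Schedule, makes 6 weeks govern off treatment too. That reading is possible, but it leaves the 2-month sentence in two places and scan marks at visits 60 days apart. The conflict remains.

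**Conclusion.** The concern holds in limited form. The off-treatment conflict (6 weeks against 2 months) is in the text and needs no assumption. The first scan's dependence on Cycle 2 is also in the text.

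Bias between arms is conditional on unequal delay or early stopping, which the documents neither report nor rule out. If it occurs, early stopping has a small effect: HR about 0.97 to 1.01 with 10% to 50% of one arm stopping. A 2-week delay matters more at the 3-month landmark: 8.7 to 12.9 points in delayed patients, and 1.3 to 3.9 points for an arm with 10% to 30% delayed at the 2.8-month median. These sizes rest on exponential TTP and assumed fractions. They concern secondary estimates only; OS, its power and its success rule are unaffected. The change is worth making because it is cheap and two scan intervals cannot both be followed.

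**What to change.** Reconcile the synopsis, Sections 10.1 and 10.3.2.2 and Attachment 1 to one rule: tumor scans every 6 weeks (±3 days) on a calendar counted from randomization, regardless of cycle delay, drug discontinuation or time on study, until RECIST v1.1 progression, with survival contact every 2 months thereafter. In Attachment 1, take the scan mark out of the generic Cycle 3,n Day 14 and 60-day columns and let the row's comment carry the rule. State that footnote a does not apply to tumor scans. Align SAP Section 6.12.7.3.

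The cost is protocol wording and a table edit. Some scans will no longer coincide with a cycle visit or a 60-day visit, and patients off drug will be scanned every 6 weeks, which Section 10.1 already asks for.

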#### **10.1.1. Clinical Efficacy Measures**

While RECIST version 1.1 is the primary efficacy measure, other radiographic assessments will be used in the study. RECIST version 1.1 (see [Attachment 9](#)) and mRECIST ([Attachment 16](#)) will be used for response assessment; RECIST version 1.1 will also be used for TTP, and PFS. irRECIST (Wolchok et al. 2009; see [Attachment 17](#)) may be used for explorative response assessment and time-to-event variable determination.

Each patient will be assessed by 1 or more of the following radiologic tests for tumor measurement at the times specified in the Study Schedule ([Attachment 1](#)): CT scan or MRI. In addition, for final study report analyses, a central review of all radiographic examinations will be conducted, and assessments of progression will be based on RECIST v1.1 and, if applicable, irRECIST.

Radiologic assessments will be collected at the times shown in the Study Schedule. MRI and/or CT scans will be collected and stored centrally.

Changes in biomarkers response (collected as specified in the Study Schedule [[Attachment 1](#)] and detailed in Section [10.4.2.2](#)) are measures of progressive disease response, and the relationship to clinical efficacy measures will be explored.

